Study Protocol

IRB ID: 20180597 (CR00012479)

Study Number: 1 R34 DA043784-01A1

Date: July 19, 2018

Study Title

Culturally Modified Family Based Therapy for Haitian Youth in South Florida
(CIFFTA).

NCT number: 03876171

Date: July 19, 2018

INSTRUCTIONS:

1) Protocol Title

Culturally Modified Family Based Therapy for Haitian Youth in South Florida (CIFFTA).

2) IRB Review History*

None

3) Objectives*

The study will pursue the following Specific Aims:

Aim 1. To adapt CIFFTA and the assessment instruments necessary to test its efficacy to the unique Haitian sociocultural contexts. This process of adaptation has the purpose of optimizing CIFFTA's acceptability and cultural appropriateness. It will rely on ethnographic methods (participant observations, focus groups, and interviews) to guide the adaptation process.

Aim 2. Determine, via a pilot efficacy trial, the impact of CIFFTA compared with standard-of-care for reduction of drug use, risky sexual behaviors, and delinquency risk among Haitian adolescents ages 13 to 17 in Miami-Dade County. The ethnographic component of the study will monitor the delivery of the intervention, collecting process data, and affording the investigators needed perspective on the intervention's impact.

Aim 3. To generate preliminary data on the usefulness of assessment tools and CIFFTA's efficacy among the population. These data will help evaluate the effect of the intervention and its best form of implementation. They will also provide preliminary evidence to justify a full clinical trial of CIFFTA in a population of at-risk Haitian youth.

Primary study outcomes include: intervention attendance and completion; sustained abstinence in substance use through biochemical verification and self-report; family functioning; sexual risk behavior; and conduct disorder. Secondary outcomes include: recidivism in delinquency, improvement in family communication, and peer/gang involvement. Outcomes will be assessed through follow-up instruments at three points: 3, 6 and 12 months.

4) Background*

Despite preventive efforts made over the last three decades, it is clear that some populations have not benefited from attempts to deter them from risky behaviors. Haitian youth constitute an important but understudied population who may be particularly

Study Protocol

IRB ID: 20180597 (CR00012479)

Study Number: 1 R34 DA043784-01A1

Date: July 19, 2018

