difficult to “reach” via the usual preventive and intervention strategies due to circumstances of immigration, poverty, and marginalization.

This study will develop and implement a culturally specific, family-based individual, drug use, sexual risk and delinquency risk reduction program for Haitian adolescents aged 13-17 in Miami-Dade County. First, instruments for the intervention will be pretested with 10 Haitian youth and their families and then refined based on cultural acceptability interviews and focus group data. Second, we will conduct a pilot randomized trial with 88 at-risk Haitian youth and their families. We will test the CIFFTA model against the Standard of Care currently being offered by the Miami-Dade’s Juvenile Service Department (JSD) to Haitian adolescents in their diversionary program. The goal of the pilot study is to obtain preliminary data on CIFFTA’s feasibility, cultural acceptability and efficacy.

Research activities will include recruitment of Haitian families whose youths are in the JSD program in Miami-Dade Juvenile Justice System; participant observation in households of recruited families in Miami, Homestead, and Florida City; modification of CIFFTA for use in Haitian families; implementation of a pilot intervention in a limited number of youth and their families; process and outcome evaluation of those interventions; analysis of data resulting from these activities; and design of an intervention to be applied on a larger scale after completion of the present project.

5) Inclusion and Exclusion Criteria*

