This is a multi-wave study, with approximately all the participants recruited by the end of Year 02 and the remainder in the beginning of Year 03. At baseline, we will conduct comprehensive assessments of all study constructs and repeat all other assessments annually. Activities during the first three months will consist of the following: Staffing, Instrument Calibration, Ethnographic Update. Each wave will be composed of 22 participants to be randomized into two groups (11 each). Each undergo assessment at intake (T1) and outtake (T2), a booster session 3 months after outtake and a final assessment at 12 months. Data analysis process will be initiated at the third month and continue throughout the study implementation.

Study Protocol

[figure not shown]
IRB ID: 20180597 (CR00012479)

Study Number: 1 R34 DA043784-01A1

Date: July 19, 2018

Publications are expected to start from month 20. The table below details the activity processes.

Project Timeline

9) Study Endpoints*

Primary outcomes are: intervention attendance and completion; sustained abstinence in substance use through biochemical verification and self-report; family functioning; sexual risk behavior; and conduct disorder.

Secondary outcomes include recidivism in delinquency, improvement in family communication, and peer/gang involvement.

10) Procedures Involved*

RCT procedures

CIFFTA has three major components – Family-Based Therapy, Individual Therapy, and Psycho-educational Modules – delivered over 16 weeks in a six sessions (60 minutes each) per month format. In this study, the therapy will be delivered in the home to reduce missed sessions and premature termination. Special training will focus on how to structure the home environment to reduce distractions. Three sessions per month will typically be a session which may include Family-based Therapy or Psycho-educational modules with the family or parents alone (e.g., parent training). The other three sessions are typically with the adolescent alone and include Motivational Interviewing or Psycho-educational modules designed for the adolescent.

Study Protocol

IRB ID: 20180597 (CR00012479)

Study Number: 1 R34 DA043784-01A1

Date: July 19, 2018

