school, criminal friends, alcohol/drug use, leisure/recreation, personality/behavior, family circumstances, and attitudes/orientation) yielding overall risk scores ranging from (0-8). The YLS/CMI is administered to all juveniles processed in the JSD. The same instruments will be used to assess youth from the GRP.

Drug use and psychological adjustment will be assessed with the Comprehensive Adolescent Severity Inventory developed by Myers and colleagues (52). The CASI covers a broad range of psychosocial and risk behaviors including information on substance abuse (e.g. age of first use, current patterns of use, friends' use), criminal activity, mental health, peer relationships, family/household relationships, education, and sexual behavior. Among other things, the instrument gathers information concerning youth use of a range of substances and will be adapted to assess ATOD use at baseline and post-intervention. In this way, we will be able to determine participants' historical and recent use (i.e. past 30 days, past 3, 6, and 12 months), if any, of drugs and alcohol. Similar assessments are made of sexual risk behavior and a global assessment of psychological adjustment is included that yields a continuous measure of global functioning. Adequate levels of internal consistency, test-retest reliability and validity coefficients are reported.

Conduct Disorder. Youth problem behaviors will be measured using the Conduct Disorder instrument from a Revised Behavior Problem Checklist (53) utilized previously by BSFT staff (54). The RBPC is an empirically derived measure consisting of 89 problem behaviors. We will adapt the instrument to include behaviors that are particularly salient among Haitian youths and exclude others that are deemed less salient. For each youth, the primary caregivers will rate the severity of each behavior on a 3 point scale (0 = no problem, 1 = mild problem, 2 = severe problem). The Conduct Disorder Subscale as used for this study consists of 22 items ($\alpha = .92$) measuring the youth's disruptive behavior at home (e.g., "disobedient; difficult to control"). The Conduct Disorder Subscale will be administered at intake and again at termination.

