### ***Analytic Methods***

Latent Growth Modeling within a Structural Equation Model (SEM) framework. We will conduct latent growth curve analyses using Stata 14 gsem (1), SAS Proc Mixed (2), SPSS Mixed Models, and/or Mplus 8 (3) to compare the trajectories of participants in CIFFTA to those in TAU. Given that the data are balanced and have more than 2 time points, the model is identified, thereby allowing us to perform SEM growth curve analysis (4). These models conceptualize each component of growth (the baseline/intercept, the slope/rate of change, the quadratic slope, etc.) as composed of a fixed and random effect. Thus, these models have multiple components of variance as well as a regression-type model of the underlying mean growth curves of the two groups. Within an SEM framework, growth curves are treated as latent (unobserved) variables influenced by occasion- and individual-level covariates, allowing us to explicitly model growth trajectories overtime.

Specific analysis link functions will be matched to fit the distribution of each outcome variable. For ordinal outcomes (e.g., frequency of drug/alcohol usage), we will use an ordinal logistic regression function. The proportional odds assumption will be evaluated using the Brant test, and if needed, addressed by allowing problematic coefficients to vary across levels of the outcome variable. Count outcome measures (e.g., number of sexual partners, problem behaviors, re-arrests) will be analyzed using a negative binomial function rather than Poisson regression to address potential over-dispersion. Vuong tests will be performed to assess whether the data have an excess of zeros, and if necessary, zero inflated negative binomial regression will be used instead.

Analysis for Aims 2 and 3: The first set of analyses will explore the efficacy of CIFFTA compared to SOC in modifying the main adolescent outcomes and to generate effect sizes for a possible full clinical trial: a) drug/alcohol use, b) risky sexual behavior, c) delinquent behavior, and d) recidivism. Latent growth modeling will be used to investigate the efficacy of CIFFTA as compared to SOC. For each model, we will examine the effect sizes to determine the overall impact of CIFFTA over SOC on the outcome variables. We will generate estimates of effect sizes, such as Cohen's d (5), for both rate of change and for the

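### The SAP's four main outcomes do not match the protocol's five primary outcomes: recidivism is secondary in one and main in the other, and attendance/completion has no analysis in the SAP text reviewed

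*SAP*

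**What the plan says.** Protocol Section 3 (Objectives) states: "Primary study outcomes include: intervention attendance and completion; sustained abstinence in substance use through biochemical verification and self-report". The list continues with "family functioning; sexual risk behavior; and conduct disorder". Section 9 (Study Endpoints) gives the same five, then adds: "Secondary outcomes include recidivism in delinquency, improvement in family communication, and peer/gang involvement". Section 3 ranks recidivism in the same way. On timing, Section 3 says: "Outcomes will be assessed through follow-up instruments at three points: 3, 6 and 12 months". Section 4 (Background) gives the goal of the pilot as preliminary data on "feasibility, cultural acceptability and efficacy".

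The SAP, in its analysis for Aims 2 and 3, lists the main adolescent outcomes as "a) drug/alcohol use, b) risky sexual behavior, c) delinquent behavior, and d) recidivism". Efficacy is compared and effect sizes for a later trial are generated on these. The mediation hypotheses that follow use the same four outcomes, with family connectedness, acculturation and motivation to change as mediators. The SAP declares no primary or secondary rank and does not mention the protocol's list.

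The protocol has two further lists. Section 10 (Study Process) anticipates effects on re-offending risk, re-arrest, drug and alcohol use, psychological adjustment, family functioning and caregiver-reported conduct. Section 12 (Data Management) lists drug use, delinquency, family functioning, school performance and psychological functioning, with a general menu of models. It promises that significance levels will be adjusted for multiple outcomes, but names neither the family of outcomes nor the method.

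**The concern.** A pilot of this kind decides which outcomes and effect sizes go into the full trial (Aim 3). If the protocol and SAP rank outcomes differently, the main result can be chosen after the data are seen, and a reader cannot tell which list governs. Here a protocol-secondary outcome would be presented as main and used to plan the next trial. Attendance and completion, the protocol's first-named primary and the most direct measure of feasibility, would have no planned analysis. Family functioning would not be reported as an endpoint. The multiplicity adjustment also has no defined family while the lists compete.

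**Working it through.** No plan figure has to be reproduced; the check is a comparison of texts. Part of the SAP ahead of its analytic methods was not in the copy reviewed, so absence is claimed only for the text supplied.

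**1. Protocol primaries traced into the SAP**

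| Protocol primary (Sections 3 and 9) | Where the SAP has it | Match |
|---|---|---|
| Attendance and completion | Not an analysed endpoint anywhere | None |
| Sustained abstinence, urine plus self-report | Ordinal frequency of use; hazard of use after the intervention | Same domain, different endpoint |
| Family functioning | Nearest construct, family connectedness, as a mediator | CIFFTA's effect on it is estimated, but not reported as an endpoint |
| Sexual risk behavior | Listed main outcome | Direct |
| Conduct disorder | Only through problem behaviors: an example of a count outcome, and a hazard analysis of other problem behaviors | Not a listed main outcome |

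The link in the last row rests on Protocol Section 10, which says: "Youth problem behaviors will be measured using the Conduct Disorder instrument". Tally: 1 direct + 1 in another form + 1 reached indirectly + 1 as mediator + 1 absent = 5.

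**2. SAP main outcomes traced back to Section 9**

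- Risky sexual behavior: primary.
- Drug/alcohol use: same domain as a primary, different endpoint.
- Delinquent behavior: follows Aim 2, which speaks of delinquency risk, but is not named in Section 9.
- Recidivism: secondary.

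Tally: 1 + 1 + 1 + 1 = 4.

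**3. Number of competing lists.** Sections 3 and 9 agree with each other. Section 10, Section 12 and the SAP each differ from them and from one another, so there are four lists. Section 10 includes re-arrest and family functioning, but not attendance or sexual risk. Section 12 includes family functioning, but not attendance or sexual risk.

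**4. Timing of the conduct measure.** Section 10 schedules the Conduct Disorder Subscale at intake and termination, which is two occasions. The SAP justifies its growth model by saying that there are more than two. For a continuous outcome, two occasions give 2 means + 3 variances and covariances = 5 moments. A linear growth model with random intercept and slope needs 2 means + 2 variances + 1 covariance + at least 1 residual variance = 6 parameters. Adding treatment arm as a predictor adds two of each (7 against 8), so the model stays unidentified. The schedule and the model do not fit for this subscale.

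**5. Abstinence.** The rule in Section 12 (urine tests) classifies use or no use, drug by drug, at each data collection point. With kappa below .80, either a positive test or reported use counts as use. With kappa above .80, self-report alone is used; kappa of exactly .80 is not assigned. The rule does not say how occasions combine into sustained abstinence. Its high-kappa branch also drops the biochemical component that Sections 3 and 9 require.

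**The case against.** The SAP writes of main adolescent outcomes, not primary outcomes. Attendance is a delivery measure and family functioning is partly caregiver-reported, so a list of adolescent outcomes could leave both out. That carries some weight for attendance. It does not explain why recidivism is included, or why conduct disorder is missing when Section 10 (Instrumentation) counts it, and family functioning, among the youth constructs.

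The SAP list also has roots in the protocol: three of its four outcomes follow Aim 2, and recidivism appears in Section 10. This stands. A reader might infer that the SAP departed on its own from a settled protocol, but the documents do not support that, because the protocol is inconsistent within itself.

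Three other stronger readings also fail:

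- That conduct disorder and family functioning are dropped altogether. The SAP plans two kinds of analysis for problem behaviors, the mediation model estimates CIFFTA's effect on family connectedness, and Section 12 names family functioning as an outcome.
- That conduct cannot be followed over time. Section 10 also has parent and youth behavior checklists with a conduct-problems scale, and a risk inventory with a conduct domain. These may be collected at follow-up, and the timeline figure is not available. The misfit is specific to the subscale.
- That a confirmatory claim is undermined. The SAP describes its analyses as preliminary.

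**Conclusion.** The mismatch holds and should be fixed. One of five protocol primaries is a main SAP outcome as stated, four are not, and one of four SAP main outcomes is secondary in the protocol. The placement of recidivism and the difference between the lists are read directly from the text and need no assumption. The absence of an attendance/completion analysis holds for the SAP text supplied. A reader might infer that these data would go unreported, but the documents show only that no analysis is planned there. The conduct disorder mapping assumes that the SAP's problem behaviors means the measure described in Section 10. Sample size and power do not enter, because they do not measure a mismatch of outcomes.

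**What to change.** Before analysis, adopt one outcome hierarchy across Protocol Sections 3, 9, 10 (Study Process) and 12 and the SAP. Either align the SAP's main analyses with Section 9 or amend Section 9, and state where recidivism ranks.

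If Section 9 stands:

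- List family functioning and conduct disorder as outcomes, each with its own between-arm comparison. For the Conduct Disorder Subscale, use a baseline-adjusted contrast at termination if only two occasions are collected, and say which conduct measures, if any, are taken at follow-up.
- Report attendance/completion as a proportion with its confidence interval.
- Define sustained abstinence so that it uses both urine results and self-report across the follow-ups. Reconcile this with the Section 12 rule that uses self-report alone when kappa exceeds .80, and assign the case of exactly .80.
- Keep recidivism secondary.

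Apply the multiplicity adjustment promised in Section 12 to the reconciled list, naming the family and the method. The cost is rewording in both documents and a few added models.

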CIFFTA uses a flexible manual that allows for tailoring of the intervention through the selection of psycho-educational modules that address specific family and adolescent clinical and cultural issues that are central to that lives of that family. Individual and family level targets of change must be specifically able to address the ecological factors as well. For example, parenting practices may be improved to better monitor the adolescent's peers; parental leadership and guidance may focus on taking a more active role in advocacy in schools and in teaching adolescents how to handle racism and discrimination; and adolescent skills may become important in better addressing peer pressure in the peer context.

Overall intervention process.

Study Protocol

IRB ID: 20180597 (CR00012479)

Study Number: 1 R34 DA043784-01A1

Date: July 19, 2018

Pretest. CIFFTA instruments only will be pretested with a subsample of 5 Haitian youths and their families. Youths and families will be selected purposefully and will NOT be included in the study sample. Because the whole trial is consist of testing the applicability of CIFFTA within this population, the study will not be tested prior implementation. The instruments will be tested for fidelity of translation.

Study Process. Randomization will be done after baseline data are logged and will be carried out via computer-generated sequential assignment; in that sense, interventionists do not control randomization and interviewees will be blind to condition. At baseline, we will conduct comprehensive assessments of all study constructs and repeat all other assessments (see timeline). Outcomes anticipated will include lowered risk for re-offending (i.e. YLS scores), rates of recidivism (i.e. re-arrest), drug/alcohol use, and improved psychological adjustment and family functioning of those youths in the intervention group relative to those in the comparison group. Similarly, we expect parents/caregivers of these youths to see improvement in their child's behavior (i.e. less conduct disorder reported) and improved family functioning overall.

Ethnography.

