difference at a particular time between the two conditions (6). Following Cohen's guidelines (5), we will interpret our effect sizes using the convention of "small" ( $d = .2$ ), "medium" ( $d = .5$ ), and "large" ( $d = .8$ ).

Our hypotheses concerning the direct and indirect effects of key variables on drugs/alcohol use, risky sexual behavior, delinquent behavior, and recidivism will be tested using SEM mediation analyses. To test potential indirect relationships we will include several mediators, including family connectedness, acculturation (bicultural involvement scale), and motivation to change. This will allow us to examine whether CIFFTA directly effects our outcomes of interest and/or whether the effect of CIFFTA operates through its effect on family connectedness, acculturation, and motivation to change. These mediation models will enable us to address **Specific Aim #2** by testing the significance of paths in the model linking the intervention variable to the risk-related outcomes in question (both at discrete points in time and as the change index derived from differences in ordinal frequency at baseline and at post-intervention time intervals).

In a separate set of analyses, we will examine the hazard rate of drug/alcohol use and sexual risk behavior during the post-intervention phase of the study. Comparisons across the two intervention conditions will thus be made regarding the hazard rate of having sex during the post-intervention period, sex with multiple partners ( $>1$  per month), and unprotected sexual episodes. Specifically, shared frailty Cox proportional hazard regression will be utilized to examine possible differences in the hazard rate of various risky behaviors (drug- and sex-related) in CIFFTA and control conditions during the post-intervention phase. This will prove particularly helpful in determining the hazard rate for post-intervention sexual initiation or unprotected sex in the two groups being compared, while also controlling for the time-dependence nature of our data. Similar analyses will be performed regarding initiation into drug use and other problem behaviors to determine whether the possible benefits of the CIFFTA approach extend to a range of risky behaviors.

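### Recidivism goes through the growth model with no defined re-arrest window or baseline; if counted after entry, a constant proportional reduction can leave the rate-of-change effect near zero

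*SAP*

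**What the plan says.** The SAP (Analytic Methods, analysis for Aims 2 and 3) names the outcomes to be analysed and to supply effect sizes for a possible full trial: "a) drug/alcohol use, b) risky sexual behavior, c) delinquent behavior, and d) recidivism". It then states: "Latent growth modeling will be used to investigate the efficacy of CIFFTA as compared to SOC". The growth components are "the baseline/intercept, the slope/rate of change, the quadratic slope, etc".

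For the distribution it says: "Count outcome measures (e.g., number of sexual partners, problem behaviors, re-arrests) will be analyzed using a negative binomial function rather than Poisson regression", with a zero-inflated version if needed. Cohen's d is to be estimated "for both rate of change and for the" "difference at a particular time between the two conditions".

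The protocol (section 10, Study Process) anticipates lower "rates of recidivism (i.e. re-arrest"), and section 9 lists recidivism as a secondary outcome. Neither document states when counting of re-arrests starts, how long each window is, what the baseline value is, whether there is an exposure offset, or whether the arms share an intercept. The SAP's survival analyses name drug and sexual risk behaviours and other problem behaviours, but not re-arrest.

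**The concern.** A growth model suits a measure such as a symptom score, which every youth has before treatment: the arms start level, and treatment appears as diverging slopes. Re-arrest, read as a new event after entry, has no pre-treatment value of that kind. The first count already falls in a period that treatment may have affected. If CIFFTA lowers the re-arrest rate by the same factor throughout follow-up, the arms differ from the first window and the gap on the log scale does not widen. The slope contrast then asks whether the rate ratio changes over time, which is a different question from whether CIFFTA reduces re-arrest.

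The SAP intends these effect sizes to inform a full trial. A rate-of-change d near zero could be carried forward as evidence of no effect when re-arrest had been halved.

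**Working it through.** The documents give no figure for the recidivism effect, so there is none to reproduce. The SAP's one power statement concerns R² and does not bear on this point.

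**Inputs from the documents.** 80 youths analysed, 1:1, so 40 per arm (SAP, Power Analysis; Protocol section 8). Intervention of 16 weeks, taken as about 4 months. Follow-up at 3, 6 and 12 months after the intervention ends (Protocol section 10). Windows from randomisation are therefore 0-4, 4-7, 7-10 and 10-16 months.

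**Assumed, because not given.** Log link; SOC re-arrest rate of 0.5 or 1.0 per youth-year; gamma frailty variance of 0.5 or 1; constant rate ratio of 0.5; two-sided 5% test.

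**Step 1, algebra.** With arm a = 0 or 1 and time t, write log(rate) = α + βt + a(γ + δt). A constant rate ratio ρ requires γ + δt = log ρ at every t, so γ = log ρ and δ = 0. For ρ = 0.5, γ = −0.693.

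**Step 2, fit to expected counts.** At an assumed 0.05 per month, windows of 3, 3 and 6 months give SOC counts of 0.15, 0.15 and 0.30, and CIFFTA counts of 0.075, 0.075 and 0.15. The ratio is 0.5 in each. These are mean models without random growth terms.

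| Parameterisation | Arm-by-time slope (log, per month) |
|---|---|
| Separate intercepts, Poisson, with or without a row of baseline zeros | 0.000 |
| Separate intercepts, negative binomial with offset | 0.000 |
| Separate intercepts, negative binomial without offset | +0.0003 |
| Separate intercepts, negative binomial with baseline zeros included | −0.0015 |
| Shared intercept | −0.066 to −0.070 |
| Equal non-zero baseline, with offset | −0.048 |
| Index arrest coded 1 at baseline | −0.104 to −0.121 |

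In the first four rows the arm intercept is between −0.683 and −0.695, so it carries the effect.

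**Step 3, how many events each contrast has.** Expected events at ρ = 0.5 are 40 × rate × years × (1 + 0.5):

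- Last window, 0.5 year: 15 at the lower rate, 30 at the higher.
- Three follow-up windows, 1 year: 30 and 60.
- From randomisation, 16/12 years: 40 and 80.

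**Step 4, simulated power** over the four combinations of rate and frailty variance (log-link models, standard errors clustered on youth):

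| Contrast | Rejects |
|---|---|
| Arm-by-time slope, separate intercepts | 5-7% |
| Model-implied difference near mid follow-up | 32-58% |
| Model-implied difference at the last visit | 21-44% |
| Total count, same three windows | 35-63% |
| Total count from randomisation | 45-72% |

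The slope test rejects at about its nominal level although the true rate is halved. The last row includes the four treatment months, so part of its gain is additional data. The like-for-like comparison is with the 35-63% row.

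**The case against.** A reader might go further and infer that no youth has a re-arrest at baseline, that the rate-of-change effect is therefore exactly zero, and that the plan would miss a real reduction. The documents do not support this.

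- **Baseline.** Nothing says the baseline value is zero. Criminal history is a youth construct, study constructs are assessed at baseline (Protocol section 10), and prior history is a criterion for diversion (Protocol section 21). Earlier arrests could be counted, and a non-zero baseline gives a non-zero slope.
- **Exactly zero.** This needs post-entry counting, a log link, separate arm intercepts and a constant ratio. The SAP fixes none of the first three. Equal intercepts are a natural constraint in a randomised growth model and would move the effect into the slope. An effect that builds or fades would also appear there.
- **Effect lost.** The SAP also estimates the difference at a particular time. That is a model-implied contrast drawn from all waves, not a regression on one window, and near mid follow-up it almost matches the total over the same windows.
- **Weight.** Recidivism is secondary in the protocol, and the SAP calls its analyses preliminary.

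All of this stands as a limit on the point. It does not remove it. A shared intercept placed at the first follow-up window imposes equality at a time treatment may already have affected. Coding prior or index arrests as baseline makes the slope depend on a choice the SAP does not make: across the codings above it runs from about zero to −0.121 for the same true effect.

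**Conclusion.** The point holds in conditional form. For post-entry re-arrest counts under a log link with separate arm intercepts, the rate-of-change effect size is close to zero for a constant proportional reduction, and its test has 5-7% power against a halved rate. The plan as a whole does not lose the effect, because the difference at a particular time would show it. The power of that contrast, however, runs from 21-44% to 32-58% according to a time the SAP does not specify. A total count gives 35-63% on the same follow-up and 45-72% from randomisation.

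The power figures rest on assumed rates, frailty and rate ratio; none is in the documents. The near-zero slope does not depend on the event rate, but it does depend on the ratio being constant. The case for change is that a simpler measure answers the intended question directly and does not depend on unstated coding.

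**What to change.** For recidivism, state in the SAP that the effect measure is one total re-arrest count per youth over a single fixed window from randomisation, analysed by negative binomial regression with an exposure offset and reported as a rate ratio with its 95% interval. Define a countable re-arrest, its data source and the window length. Report time to first re-arrest from randomisation as support. Do not use the rate-of-change d as the effect size for this outcome. The growth model can stay for outcomes with a genuine baseline measurement.

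The cost is SAP wording and a simpler model, with no new data. The downside is that there would be no trajectory estimate for re-arrest.
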